6.3.1.2.2. Primary Analysis for Superiority

If the NI of mRNA-1010 vs. active comparator is demonstrated using the PP Set, superiority of mRNA-1010 vs. active comparator will be evaluated using the same primary endpoint based on the mITT Set, either at IA or at the final analysis.

Superiority of mRNA-1010 vs. the active comparator on the primary efficacy endpoint will be concluded if the one-sided p-value for rejecting $H_0^2: HR \geq 1$ (equivalently, $H_0^2: rVE \leq 0\%$) is less than the nominal alpha based on the Lan-DeMets Pocock approximation spending function, based on the mITT Set. For this superiority testing, the nominal one-sided alpha level will be 2.07% at IA, and 1.20% at the final analysis, respectively, if the IA is conducted when exactly 75% of total number of cases are observed.

As for the primary NI analysis, the following sensitivity analyses for the primary superiority analysis will be conducted: 1) the superiority analysis will be repeated on the PP Set using the same methods as described above; 2) the superiority analysis of the primary efficacy endpoint will also be performed using the actual stratification factors (CRF-derived) on the mITT Set; 3) the superiority analyses will be performed on the mITT Set by excluding RT-PCR confirmed protocol-defined ILI co-infected with other respiratory viruses as confirmed by RT-PCR respiratory test panel (see Section 6.3.1.2.1).

6.3.1.2.3. Supportive Analyses

As a supportive analysis, rVE will be estimated by one minus the ratio of incidence rates (mRNA-1010 vs. active comparator) multiplied by 100%:

$$rVE = 100 \times (1 - \text{ratio of incidence rates adjusting for person-time}) \%$$

The 95% CI of rVE will be computed using the exact method conditional upon the total number of cases adjusted by the total person-time.

For each participant, the person-time is calculated as the time (days) from randomization to the date of the first episode for participants with a case, and the time (days) from randomization to the date of censoring for participants without a case (or who are censored). Then each participant's person time is adjusted by 180 days to obtain person-season, i.e.

$$\text{person-season} = \text{person-time} / 180.$$

The total number of person-seasons for each vaccination group is the sum of the individual person-seasons in the vaccination group.

The incidence rate per 1000 person-seasons for each vaccination group will be calculated as the number of participants with a case (i.e., first episode of RT-PCR confirmed protocol-defined ILI at least 14 days post vaccination and up to Day 181 (Month 6) or end of the influenza season, whichever occurs later) divided by the total person-season in each vaccination group multiplied by 1000. The same censoring rules as described for the primary analyses will be followed.

Summaries of total person-season and incidence rate, and 95% CI for incidence rate, will be provided by vaccination group. The 95% CI of the incidence rate will be calculated using the exact method (Poisson regression) and adjusted by person-time.

A stratified log-rank test will be performed to assess the time to first episode of RT-PCR confirmed protocol-defined ILI starting 14 days post vaccination up to Day 181 or at the end of the influenza season.

A Kaplan-Meier curve will be used to plot the estimated cumulative incidence rates over time by vaccination group. Cases of RT-PCR confirmed protocol-defined ILI will be counted starting 14 days post vaccination up to Day 181 or at the end of the influenza season, whichever occurs later. The same censoring rules as described for the primary analyses will be followed.

In addition, supportive analyses will be conducted using similar stratified Cox proportional hazard analyses to estimate the rVEs, defined as the percent reductions in the hazards (mRNA-1010 vs. active comparator), i.e. $rVE = 100 \times (1 - HR) \%$, together with the 95% CIs, to prevent the occurrences of the following events:

1. RT-PCR confirmed protocol-defined ILIs caused by influenza A by different subtype:
 - RT-PCR confirmed protocol-defined ILIs caused by influenza subtype A/H1 per RT-PCR starting 14 days post vaccination up to Day 181 or at the end of the influenza season, whichever occurs later;
 - RT-PCR confirmed protocol-defined ILIs caused by influenza subtype A/H3 per RT-PCR starting 14 days post vaccination up to Day 181 or at the end of the influenza season, whichever occurs later;
 - RT-PCR confirmed protocol-defined ILIs caused by influenza A per RT-PCR with unknown subtype starting 14 days post vaccination up to Day 181 or at the end of the influenza season, whichever occurs later.

The time to the first episode will be calculated as: Start date of the first RT-PCR confirmed protocol-defined ILI with the specified RT-PCR subtype – Date of randomization +1.

Similar censoring rules as for the primary efficacy endpoint will be applied. Additionally, for an RT-PCR confirmed protocol-defined ILI case, if the subtype is different from the one being analyzed, the participant will be censored at the start date of the confirmed ILI case.

2. Positive RT-PCR cases regardless of ILI symptoms, starting 14 days post vaccination up to Day 181 or at the end of the influenza season, whichever occurs later.

For this analysis, the time to the first event will be calculated as: The first positive RT-PCR date – Date of randomization +1. Similar censoring rules as for the primary efficacy endpoint will be applied.

Supportive analyses will be performed in the PPS set, and in the mITT set if the NI test is successful.

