4.3. Sample Size and Power

This Phase 3 study will plan to randomize approximately 23,000 participants in a 1:1 ratio to the mRNA-1010 or the active comparator groups. Therefore, approximately 11,500 participants will be randomized to each group.

The sample size is driven by the total number of cases to demonstrate rVE (mRNA-1010 vs. active comparator) to prevent the first episode of RT-PCR confirmed protocol-defined ILI caused by any influenza A or B virus strains.

Under the assumption of proportional hazards and with 1:1 randomization of mRNA-1010 and active comparator, a total of 365 cases in the PP Set will provide at least 93% power to establish a NI claim with a NIM = 10%, i.e., rejecting the null hypothesis $H_0^1: rVE \leq -10\%$,

with one IA using the Lan-DeMets Pocock boundary for efficacy and a log-rank test statistic with an overall one-sided Type I error rate of 2.5%.

The number of cases will be continuously monitored using external epidemiologic data (e.g., CDC.gov). It is projected that by middle of February 2023, approximately 274 cases (75% of the targeted cases) will be observed in the PP Set. In the scenario that fewer cases are observed by middle of February, the IA will still be conducted around this timeframe because of the seasonality of influenza in the Northern Hemisphere, and the nominal alpha to be spent at the IA and final analysis will be adjusted accordingly.

The total number of cases pertains to the PP Set accruing at least 14 days after study intervention. Approximately 23,000 participants will be randomized with the following assumptions:

- The target rVE of mRNA-1010 to the active comparator is 25% to prevent the first episode of RT-PCR confirmed protocol-defined ILI caused by any influenza A or B virus strains.
- An attack rate of 2% in the active comparator for the primary endpoint.
- One IA in the middle of February 2023 with approximately 75% of total target cases expected across 2 study intervention groups in the PP Set.
- A dropout rate ~ 10% (not evaluable for the PP Set).
- Type I error rate will be adjusted using the Lan-DeMets Pocock boundary.

If the IA is conducted exactly at 75% of total target cases, the nominal one-sided Type I error rate will be 2.07% at IA, and 1.2% at the final analysis for NI testing, respectively.

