6.3.1.1. Primary Efficacy Endpoint Definition/Derivation

The primary efficacy endpoint is the rVE of mRNA-1010 as compared to the active comparator to prevent the occurrence of the first episode of RT-PCR confirmed protocol-defined ILI starting 14 days post vaccination and up to Day 181 (Month 6) or the end of the influenza season, whichever occurs later, caused by any seasonal influenza A or B virus strains regardless of antigenic match to strains selected for the seasonal vaccine.

The derivation rules to identify the first episode of RT-PCR confirmed protocol-defined ILI (see the definition in [Section 3.1.2](#)) are given below:

- **CCI** [REDACTED]
[REDACTED]
[REDACTED]
 - [REDACTED]
[REDACTED]
[REDACTED]
 - [REDACTED]
- [REDACTED]
[REDACTED]
[REDACTED]
[REDACTED]
- [REDACTED]
[REDACTED]
 - [REDACTED]
[REDACTED]
 - [REDACTED]
[REDACTED] [REDACTED]
[REDACTED]

The start date is the earliest date of the ILI symptom onsets (within 7 days prior to or on the same day as the positive RT-PCR date).

- If multiple episodes are identified, the first episode of RT-PCR confirmed ILI is the one with the earliest start date.

The time to the first episode of RT-PCR confirmed protocol-defined ILI, in days, will be calculated as: Start date of the first RT-PCR confirmed protocol-defined ILI – Date of randomization +1.

Cases will be counted for the primary efficacy endpoint when the first episode of RT-PCR confirmed protocol-defined ILI starts 14 days after the vaccination and up to Day 181/ Month 6 or end of influenza season whichever ends later, i.e.,

Vaccination date + 14 \leq Start date of the first RT-PCR confirmed protocol-defined ILI \leq Date of Day 181/ Month 6 or at the end of the influenza season, whichever occurs later.

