Participants without RT-PCR confirmed protocol-defined ILI will be censored at Day 181 (Month 6) or the end of the influenza season (whichever occurs later), or at the data cutoff date for interim analysis, or at the date of early discontinuation or death unrelated to influenza, whichever is earliest. Participants with early RT-PCR confirmed protocol-defined ILI up to 14 days after the study vaccination (i.e., start date of the RT-PCR confirmed ILI \leq vaccination date +13) will be censored at the start date of the early RT-PCR confirmed protocol-defined ILI.

The trial will be considered to meet the primary efficacy objective by demonstrating NI of mRNA-1010 to the active comparator if the one-sided p-value for rejecting $H_0^1: HR \geq 1.1$ (equivalently, $H_0^1: rVE \leq -10\%$) is less than the nominal alpha based on the Lan-DeMets Pocock approximation spending function, based on the PP Set. The nominal one-sided alpha level will be 2.07% at IA, and 1.2% at the final analysis, respectively, if the IA is conducted when exactly 75% of the total number of cases are observed.

As sensitivity analyses, the primary endpoint analysis for NI will be repeated on the mITT Set using the same methods as described above. The NI analysis of the primary efficacy endpoint will also be performed using the actual stratification factors (CRF derived) on the PPS Set.

Thirdly, the NI analysis will be repeated on the PP Set with co-infected cases excluded from the analyses:

- co-infection of influenza with COVID-19 and/or respiratory syncytial virus (RSV) as confirmed by the RT-PCR respiratory test panel;
- co-infection of influenza with any other respiratory virus as confirmed by the RT-PCR respiratory test panel.

Co-infections are identified from the same NP swab or two swabs collected within 3 days.

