6.3.2.2.3. Supportive Analyses

The same method used for the primary endpoint based on the incidence rate and stratified log rank test will be performed on the mITT set as a supportive analysis if the NI for the corresponding key secondary endpoint(s) is demonstrated.

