9.6. Appendix E Estimands and Estimand Specifications**Table 9: Intercurrent Event Types**

| Label | Intercurrent Event Type | Comment |
|---|---|--|
| IcEv1 (early discontinuation or death without confirmation of cases, i.e., unrelated death) | Unrelated death without documented influenza | Participants in PP Set who withdraw consent or die due to reasons unrelated to influenza will be included in primary efficacy analysis. |
| IcEv2 (early infection) | Infection starting up to 14 days after the study intervention | Participants in PP Set who experience an early influenza infection up to 14 days after the IP will be included in primary efficacy analysis. |
| Abbreviation: IcEv: intercurrent event, PP: per-protocol. | | |

Table 10: Primary Objective and Estimands with Rationale for Strategies to Address Intercurrent Events for Per-Protocol Analysis

| Objective: To demonstrate the efficacy of mRNA-1010 to prevent influenza | |
|---|--|
| Estimand Description | rVE will be measured using 1 – HR (mRNA-1010/ Fluarix) from 14 days after study intervention. A hypothetical strategy will be used for early discontinuation (e.g., withdrawal consent, deaths unrelated to influenza) or early infection in participants in the PP Set. |
| Target Population | Adults aged 50 years and older |
| Variable/Endpoint | 
Time-to-first episode of RT-PCR confirmed protocol-defined ILI:
 
 • For participants who experience at least one RT-PCR confirmed protocol-defined ILI, this will be the number of days from the date of randomization to the earliest start date of RT-PCR confirmed protocol-defined ILI. If the earliest start date is < 14 days following randomization, the value will be censored. • For participants who do not experience RT-PCR confirmed protocol-defined ILI, this will be the number of days from the date of randomization to the earliest date of: 
 ○ early discontinuation or death unrelated to influenza ○ Day 181/Month 6 or the end of the influenza season (whichever occurs later). 
All values for or participants who do not experience RT-PCR confirmed protocol-defined ILI will be censored.
 |
| Treatment Condition(s) | Test: mRNA-1010 Reference: Active Comparator (Fluarix®) |
| Estimand Label | Estimand 1 |
| Population-Level Summary | rVE defined as 1 - HR of mRNA-1010/active comparator |

| | |
|--|--|
| Intercurrent Event Strategy | |

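### The supportive incidence rate counts cases only from day 14 after vaccination but counts person-time from randomization, so each group's rate is about 7.8% below the rate for time at risk at Day 181 follow-up

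*SAP*

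**What the plan says.** SAP 6.3.1.2.3 defines a supportive rVE as one minus a ratio of incidence rates. It also commits to reporting each group's total person-seasons, its rate per 1000 person-seasons and an exact 95% CI.

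- **Denominator.** For participants with a case, "the person-time is calculated as the time (days) from randomization to the date of the first episode". For the others it runs "from randomization to the date of censoring for participants without a case (or who are censored". Days are divided by 180 to give person-seasons.
- **Numerator.** Only a "first episode of RT-PCR confirmed protocol-defined ILI at least 14 days post vaccination and up to Day 181 (Month 6" or the end of the season counts. SAP 6.3.1.1 gives the same rule for the endpoint: "Cases will be counted for the primary efficacy endpoint when the first episode of RT-PCR confirmed protocol-defined ILI starts 14 days after the vaccination".
- **Early episodes.** Under SAP 6.3.1.2.1, participants with a confirmed episode up to vaccination date + 13 "will be censored at the start date of the early RT-PCR confirmed protocol-defined ILI". They never enter the numerator.
- **Estimand.** SAP Appendix E, Table 10 measures rVE "from 14 days after study intervention".
- **Key secondary endpoints.** Under SAP 6.3.2.2.3 the incidence-rate method "will be performed on the mITT set as a supportive analysis if the NI for the corresponding key secondary endpoint(s) is demonstrated".

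Protocol 9.5.1.1 calls for adjustment by person-time but gives no starting point for it.

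**The concern.** Numerator and denominator cover different periods. Randomization (SAP 4.4) and vaccination (Protocol 6.3.2) both fall on Day 1, and participants who discontinue before 14 days are outside the mITT Set and hence the PP Set (SAP 5.3, 5.4). Almost everyone analysed therefore contributes 14 days in which a countable case is impossible by definition. The exception is participants with an early confirmed episode, who contribute fewer days, none of which can yield a case. Nothing in either document removes this time.

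An event-free lead-in does no harm in the Cox model, the log-rank test or the Kaplan-Meier curve, because it adds no event times and no comparisons. In an absolute rate it goes straight into the denominator. At stake are the reported group rates, their exact CIs and the person-season totals, which would understate incidence over the period in which cases can be counted.

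**Working it through.** **Inputs**

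- 23,000 randomized 1:1; about 10% not evaluable for the PP Set and 4% for the mITT Set (SAP 4.3).
- "An attack rate of 2% in the active comparator for the primary endpoint"; target rVE 25% (SAP 4.3), so 2% and 1.5% by group.
- 180 days per person-season (SAP 6.3.1.2.3).
- Non-cases followed for F days; F = 181 is follow-up to Day 181, with Day 1 counted as day 1.
- *Assumption:* case onsets uniform from Day 15 to Day F, so mean onset is (15 + F)/2. No dropout after day 14 within the analysed set.

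**The plan's own case counts**

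- mITT: 23,000 × 0.96 / 2 = 11,040 per group; 11,040 × (0.020 + 0.015) = 386.4 (stated: 386).
- PP: 23,000 × 0.90 / 2 = 10,350 per group; 10,350 × 0.035 = 362.25 (stated: 365, within 1%).

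The documents state no incidence rate, so these counts are the figures that can be reproduced. PP cases by group: 10,350 × 0.02 = 207 and 10,350 × 0.015 = 155.25, taken as 155.

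**Formulas**

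- Planned person-days T = (N − C) × F + C × (15 + F)/2
- At-risk person-days R = T − 14 × N
- Rate = 1000 × C / (person-days/180)
- Shortfall = 14 × N / T

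**Follow-up to Day 181 (F = 181, mean onset Day 98)**

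14 × N = 14 × 10,350 = 144,900 days in each group.

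- Comparator: T = 10,143 × 181 + 207 × 98 = 1,856,169; R = 1,711,269.
- mRNA-1010: T = 10,195 × 181 + 155 × 98 = 1,860,485; R = 1,715,585.

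| Group | Planned rate (exact 95% CI) | At-risk rate (exact 95% CI) | Shortfall |
|---|---|---|---|
| Comparator | 20.07 (17.43–23.00) | 21.77 (18.91–24.95) | 144,900 / 1,856,169 = 7.8% |
| mRNA-1010 | 15.00 (12.73–17.55) | 16.26 (13.80–19.03) | 144,900 / 1,860,485 = 7.8% |

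Each exact Poisson limit is a count limit divided by person-time, so both limits shift by the same factor as the rate.

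**Effect on the rate ratio (exact CI conditional on total cases)**

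- Planned: 1 − (155/1,860,485)/(207/1,856,169) = 25.29% (7.56 to 39.73).
- At risk: 1 − (155/1,715,585)/(207/1,711,269) = 25.31% (7.58 to 39.74).

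**Other lengths of follow-up (all assumed; not given in the documents)**

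| F (days) | Comparator shortfall |
|---|---|
| 240 | 5.9% |
| 210 | 6.7% |
| 120 | 11.8% |
| 90 | 15.7% |
| 60 | 23.5% |

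The first two rows represent a season ending after Day 181. The last three are possible mean follow-up times at the mid-February 2023 interim, where SAP 6.3.1.2.1 censors at the data cutoff.

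**Day-count convention.** SAP 6.3.1.2.3 does not say whether both end days count; SAP 6.3.1.1 adds 1 to its time to event. Counting inclusively gives 14/181 = 7.7% per fully followed participant, and counting exclusively gives 14/180 = 7.8%. Cases leaving follow-up at onset raise the inclusive figure to 7.8%.

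**The case against.** The strongest reply is that the SAP has simply chosen a different quantity and uses it consistently. The efficacy analysis period (SAP 6.1.7), the time-to-event variable (SAP 6.3.1.1) and the endpoint row of Table 10 all run from randomization. The Table 10 phrase about day 14 describes rVE as 1 − HR, not a group rate. The 180-day unit also fits that clock: a fully followed participant contributes about one person-season, so the planned comparator rate of 20.1 per 1000 sits next to the 2% attack rate. On the at-risk clock the rate is 21.8, and someone reading it as seasonal risk would find it roughly 8–9% high. Nothing inferential depends on the choice.

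Much of this stands. The planned figure is a valid rate per person-season since randomization, the 7.8% is a shortfall relative to a rate for time at risk, and no test or boundary uses it. The percentages for the interim rest on assumed follow-up. Mixing conventions also changes the figure: 180 days as literally planned against 167 inclusive at-risk days gives 13/180 = 7.2%, so both rates need the same convention.

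It does not remove the point. Consistency with the Cox clock is no justification where that clock is harmless in one analysis and enters the denominator in the other. The SAP text does not require the table to say that the rate includes 14 days without possible events; the table shells are not available to check. Because the shortfall varies with follow-up, a reader cannot correct interim and final rates by one common factor.

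**Conclusion.** The concern holds, as a minor one. Against a rate for the period in which cases can be counted, each group's planned rate and exact CI limits are about 7.8% low at Day 181 follow-up. The shortfall is smaller if the season ends later and larger wherever mean follow-up is shorter. The figures rest on the design attack rate and rVE, uniform case onset and no dropout after day 14; dropout after day 14 would shorten follow-up and raise the percentage slightly. The shift is nearly equal in the two groups, so the supportive rVE changes by about 0.02 percentage points and no noninferiority or superiority decision is affected.

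**What to change.** Start person-time at vaccination date + 14 for participants still at risk then: (case onset or censoring date) − (vaccination date + 14) + 1, set to zero for anyone censored earlier. Apply it to the primary endpoint and to the key secondary endpoints wherever the incidence-rate analysis is run (mITT Set, after noninferiority is shown for that endpoint). State the risk window and the day-count convention in the table footnote.

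One small drawback: if the 180-day divisor is kept, full follow-up to Day 181 becomes 167/180 = 0.93 person-season, so the rate no longer numerically equals the attack rate. The footnote should cover this. If the sponsor prefers to keep the planned denominator, the minimum is to label the rate as per person-season since randomization and note that cases count only from day 14.

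The cost is one formula in the SAP and analysis dataset, plus a footnote, using dates already collected.

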For participants aged 65 years and older, frailty will be assessed by clinic staff at baseline using the Edmonton Frail Scale (EFS).

Approximately 1000 participants will be asked to provide blood samples at baseline and on Day 29 (28 days post vaccination) for assessment of immune responses to the study intervention

(immune response biomarker subset). A clinic visit on Day 29 will be required for these participants. All participants will be asked to complete an electronic diary (eDiary) for solicited ARs from Day 1 to Day 7. All participants will be asked to provide an optional blood sample for future research use at Day 1.

There will be 6 safety telephone call visits at Days 8, 29 (except for those participants who are not in the immune response biomarker subset which requires a clinic visit on Day 29), 91, 181, 271, and 361 (Month 12)/EoS as specified in the SoE. The study duration (including screening) is up to 13 months for each participant and the total study duration is approximately 27 months (if 2 influenza seasons are required to perform efficacy analyses).

Participants will be instructed to report whether ILI symptoms have been experienced, via a Symptom Reporting eDiary, twice weekly from Day 1 to Day 181 and once weekly from Day 182 to Day 361 (Month 12)/EoS. If participants experience ILI symptoms, they will be instructed to enter the details in the eDiary and contact the clinic to determine if an NP swab should be collected for RT-PCR testing. NP swabs for testing should be collected within 72 hours of symptom onset. Sites should also reach out to participants if illness symptoms are noted upon review of the eDiary to assess whether the participant is required to provide an NP swab.

NP swab should be collected prior to any antiviral therapy if possible. NP swabs may be collected as part of a home visit in lieu of a clinic visit. In the event that NP swabs during ILI cannot be collected, any available influenza testing results performed outside of the study should be captured in the electronic case report form (eCRF).

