8.8. Efficacy Assessments

Assessment will be conducted to document RT-PCR-confirmed protocol-defined-ILI that begins at least 14 days post vaccination through Day 181 (Month 6)/end of influenza season caused by any influenza A or B virus strains or by strains similar to or antigenically matched to the strains selected for the seasonal vaccine.

Participants who develop symptoms consistent with protocol-defined ILI will have NP swabs collected for testing and ILI symptoms assessed. The initial test on the NP swab will be a real-time RT-PCR-based assay, to determine if either influenza A and/or B strains, as well as other respiratory viruses such as SARS-CoV-2, are present in the clinical sample. For samples that test positive for influenza in the RT-PCR assay, additional assays such as genetic sequencing of the virus genes and/or virus culture with subsequent antigenicity testing will be performed to determine vaccine match or similarity.

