8.9.2. Assessments for Respiratory Viral Infections

The NP swab specimen(s) for pathogens, including influenza virus, will be collected any time from Day 1 to Day 361 (Month 12)/EoS if participants have protocol-defined ILI ([Section 8.10.5](#)) or if deemed necessary per Investigator's discretion when influenza is suspected. If participants experience these signs or symptoms, they will be instructed to contact the clinic to determine if they need an NP swab collected for testing. NP swab collection should occur within 72 hours of symptom onset. Sites may follow up with participants for symptom review if illness symptoms are noted upon review of the Symptom Reporting eDiary to assess whether the participant is required to provide an NP swab. NP swab should be collected prior to any antiviral therapy, if possible. NP swabs may be collected as part of a home visit in lieu of a clinic visit. In the event that NP swabs during ILI cannot be collected, any available influenza testing results performed outside of the study should be captured in the eCRF.

Participants who experience protocol-defined ILI ([Section 8.10.5](#)) must have NP swabs collected for RT-PCR testing of influenza virus and other respiratory pathogens. For participants who experience ILI symptoms but have not yet fulfilled protocol-defined ILI definition, Investigators may use their discretion to perform NP swabs when influenza is suspected. If Investigator

discretion is applied, participant should be followed-up for any new symptoms following NP swab collection.

Symptoms reporting for ILI will be conducted between Day 1 through Day 361 (Month 12)/EoS as described in [Section 8.9.4](#).

All cases that meet the definition of RT-PCR-confirmed influenza infection should be captured as MAAEs along with relevant concomitant medications, hospitalizations, outpatient medical care, and details about severity, seriousness, and outcome.

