Participants will be instructed to report whether ILI symptoms have been experienced, via a Symptom Reporting eDiary, twice weekly from Day 1 to Day 181 and once weekly from Day 182 to Day 361 (Month 12)/EoS. If participants experience ILI symptoms, they will be instructed to contact the clinic and have an NP swab collected for testing within 72 hours. NP swab should be collected prior to any antiviral therapy if possible. NP swabs may be collected as part of a home visit in lieu of a clinic visit. In the event that NP swabs during

ILI cannot be collected, any available influenza testing results performed outside of the study should be captured in the eCRF.

Unscheduled clinic visits for ILI symptoms assessment and NP swab collection may be conducted. Participants who manifest protocol-defined ILI will be evaluated by real-time RT-PCR testing of NP swab specimen(s) for influenza and other respiratory pathogens.

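### The supportive rVE against any positive RT-PCR measures swab-detected influenza, not infection, because only protocol-defined ILI requires a swab; its window also follows the test date, not symptom onset

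*SAP*

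**What the plan says.** Item 2 of the supportive Cox analyses (SAP 6.3.1.2.3) takes as its event "Positive RT-PCR cases regardless of ILI symptoms, starting 14 days post vaccination up to Day 181" or the end of the season, whichever is later. Time runs from randomization to the first positive RT-PCR date. On censoring it says "Similar censoring rules as for the primary efficacy endpoint will be applied". Under those rules (SAP 6.3.1.2.1 and Appendix I), a participant with no event is followed to the later of Day 181 and season end, unless discontinuation, unrelated death or the interim cut-off comes first.

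The protocol defines who is swabbed. Section 8.10.5 defines protocol-defined ILI as temperature of at least 37.5 °C with at least one respiratory symptom. Under section 8.9.2 such participants "must have NP swabs collected for RT-PCR testing of influenza virus and other respiratory pathogens"; section 8.8 gives the same trigger. For ILI symptoms short of the definition, "Investigators may use their discretion to perform NP swabs when influenza is suspected". The Schedule of Events lists the NP swab only under unscheduled visits.

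The SAP words the swab rule differently. SAP 4.1 and Appendix A footnotes 11 and 15 tell participants with ILI symptoms to "contact the clinic and have an NP swab collected for testing within 72 hours". Protocol 4.1 tells them to "contact the clinic to determine if an NP swab should be collected for RT-PCR testing". The SAP states that it is based on Amendment 1.

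**The concern.** The event label reaches beyond what the sampling can observe. Whether an infection is seen depends on whether the illness meets a definition that needs raised temperature, and vaccination may change that. Suppose mRNA-1010 made breakthrough infection milder but no rarer. Fewer infections in that arm would trigger a required swab, more would pass as event-free time, and the model would return a positive rVE. A reader could take that as protection against infection whatever the symptoms. No passage limits the interpretation or plans to report swabbing by arm.

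A second difficulty is the date. The primary endpoint is placed in or out of its window by symptom start; item 2 has only a test date. A looser version of the primary endpoint should contain every primary case and treat early illness in the same way. As written, it need not do either.

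**Working it through.** **1. Who can become an event in item 2**

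| Infection presents as | Swab under the protocol | Result in item 2 |
|---|---|---|
| Protocol-defined ILI | Required | Event if positive in the window |
| Symptoms short of the definition | Investigator discretion | Event only if swabbed |
| No symptoms | None scheduled | Event-free unless tested for another reason |

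**2. The plan's own figures.** The documents give none for item 2. The planning base recomputes: comparator PP cases = 11,500 × 0.90 × 0.02 = 207; mRNA-1010 = 207 × 0.75 = 155; total 362, against the stated 365. Noninferiority power with 365 cases and an interim at 274 recomputes to 93.7%, as in Protocol Table 8.

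**3. Detection model.** Assume equal infection hazard in both arms (true rVE against infection 0%). Let f be the share of infections meeting protocol-defined ILI, all swabbed, and s the share of the remainder swabbed. Both are assumptions.

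Detected share d = f + (1 − f) × s. Observed HR ≈ d(mRNA-1010) / d(comparator). Observed rVE = 1 − HR.

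| f comparator | f mRNA-1010 | s | d comparator | d mRNA-1010 | HR | Observed rVE |
|---|---|---|---|---|---|---|
| 0.50 | 0.40 | 0 | 0.50 | 0.40 | 0.80 | 20% |
| 0.50 | 0.40 | 0.2 | 0.60 | 0.52 | 0.87 | 13% |
| 0.50 | 0.40 | 0.5 | 0.75 | 0.70 | 0.93 | 7% |
| 0.50 | 0.45 | 0.2 | 0.60 | 0.56 | 0.93 | 7% |

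**4. Same model, scaled to the plan's target.** Let the 25% target rVE on the primary endpoint come wholly from fewer infections meeting the definition: f(mRNA-1010) = 0.75 × f(comparator), with f(comparator) from 0.3 to 0.7.

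| s | Observed rVE (truth 0%) | Chance that the 95% CI excludes 0, at f = 0.5 |
|---|---|---|
| 0 | 25% | 78% |
| 0.10 | 18.2% to 21.6% | 64% |
| 0.25 | 11.8% to 16.9% | 43% |
| 0.50 | 5.8% to 10.3% | 18% |
| 1.00 | 0% | – |

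For the 43%: infections per arm = 207 / 0.5 = 414; detected shares are 0.625 and 0.531; events = 414 × 1.156 = 479; HR = 0.85; Φ(√(479/4) × ln(1/0.85) − 1.96) = Φ(−0.18) = 0.43.

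**5. When there is no bias.** If f is equal in the two arms, d is equal at every s and item 2 is unbiased. With f equal and a true infection rVE of 25%, the observed value is 25% at every s. If s = 1 there is no bias whatever f does.

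**6. The window.** A primary case needs vaccination date + 14 ≤ symptom start ≤ window close (SAP 6.3.1.1), and the confirming RT-PCR may fall within 7 days of onset (SAP 3.1.2). Item 2 attaches only the RT-PCR date. Take onset at vaccination date + 12 and a positive swab at + 15:

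- If the illness is short of protocol-defined ILI, the early-case rule in SAP 6.3.1.2.1 does not name it, so it counts at + 15.
- If it is protocol-defined ILI, the primary-type rule censors it at + 12, so it does not count.

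At the other end, onset on the last day of the window with a positive swab three days later is a primary case, but item 2's date falls outside the window.

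**The case against.** The strongest reply is that the SAP speaks of positive RT-PCR cases and never of infection, so efficacy against infection is the reader's gloss. In the scenario of step 3 the rVE against protocol-defined ILI is genuinely 20% (1 − 0.40/0.50), and item 2 never exceeds it. It therefore cannot manufacture support for the primary claim, which concerns disease. The item carries no alpha and sits outside the testing hierarchy. This stands, and it limits the point to what item 2 may be said to show.

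Surveillance is also active: twice-weekly symptom diary entries to Day 181, daily site review of the symptom diary, follow-up calls when symptoms appear, and capture of outside results when a study swab cannot be taken. A reader might infer that most infections outside the definition go unseen. The documents give neither the discretionary swab rate nor the share of infections outside the definition, so they do not support that.

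A reader might also infer that any illness starting before day 14 and swabbed later enters item 2. For protocol-defined ILI it does not, because the primary-type censoring applies at onset. The gap is confined to illness short of the definition.

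Nor does the SAP's broader swab wording create a second set of scoreable participants. SAP 4.1 and footnote 11 also tie testing to protocol-defined ILI, and item 2 scores any positive result however it arose. What remains is unaligned text.

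**Conclusion.** The point holds as a limit on a supportive analysis. Item 2 estimates rVE against influenza that was swabbed and found positive. It equals rVE against infection only if the arms have the same share of infections meeting protocol-defined ILI, or if swabbing is equally likely inside and outside the definition. Otherwise it is biased: upward if mRNA-1010 lowers that share, downward if it raises it.

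The illustrative false rVE is 7% to 20%, and up to 25% if the whole target effect is milder illness. Each figure rests on an assumed vaccine effect on meeting the definition and an assumed swab rate; the documents supply neither. They do not show that the bias will occur, only that the design cannot rule it out. The window mismatch is a separate, smaller defect that affects cases near either edge.

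It would be wrong to carry this over to the primary endpoint. That is a disease endpoint with a required swab, and its noninferiority and superiority decisions are unaffected.

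**What to change.** - Keep every positive result, but rename item 2 *first swab-detected RT-PCR-positive influenza, whether or not protocol-defined ILI was met*, and state that it does not estimate efficacy against infection.
- Date and window each event by symptom onset where there are symptoms, and by RT-PCR date only for positives without symptoms. State how the early-case rule applies to illness short of the definition.
- Report by arm the ILI-symptom episodes, the number swabbed and the number positive, split by whether protocol-defined ILI was met.
- Add a sensitivity analysis over the swab rate outside the definition.
- Reconcile the swab wording in SAP 4.1 and Appendix A footnotes 11 and 15 with Protocol Amendment 1.

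The cost is SAP wording, one extra table and one sensitivity analysis, using symptom-diary and swab records already collected, and a narrower supportive claim. The change makes selective detection visible; it does not remove it, because swabbing outside the definition stays discretionary.
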